## ***2 Study Objectives and Design***

### ***2.1 Objectives***

The primary objectives of this study are

[figure not shown]
1. Determine the effect of Roux-en-Y gastric bypass (RYGB) surgery on food preference using a standardised Buffet meal.
2. Determine if the changes in food preference following RYGB are mediated through changes in gut peptide following surgery.

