##### **Study Visit 1: Week -4**

1. Anthropometric assessment: Height, weight, BMI and waist circumference
2. Fasting Bloods
3. Buffet Meal
4. Post prandial bloods
5. Clinical Nutrition education session

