##### **Study Visit 2: Week 12**

1. Anthropometric Assessment: Height, weight, BMI and waist circumference
2. Fasting Bloods
3. Buffet meal
4. Post Prandial Bloods

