## **9 Statistical analysis**

Data will be analysed using GraphPad Prism (version 6.0) for Windows, GraphPad software (San Diego, CA, USA) and SPSS® (version 20.0) software (SPSS, Chicago, IL, USA). Central tendencies for patient and control group demographics, anthropometric data, caloric intake and macronutrient intake will be calculated and expressed using arithmetic mean  $\pm$  standard error of the mean or median (range), as appropriate. Differences in continuous variables between surgical and control groups will be calculated using the Student's *t* test or Mann-Whitney U test for parametric or non-parametric data, respectively. Correlative analyses will be performed using the Spearman Rho rank correlation to assess the relationship between *ad libitum* caloric intake and macronutrient intake with peri-operative weight loss and anthropometric data. Univariate analysis of factors associated with perioperative and post-surgical weight loss will be performed using Student's *t* test or one-way ANOVA for categorical variables or simple logistic regression for continuous variables. For the multivariate analysis, independent variables which were significant on univariate analysis, including standard demographic, food intake and food preference, will be entered into a multiple logistic regression model with a forward stepwise selection procedure to assess their impact on perioperative and post-surgical weight loss. All statistical analyses will be two-tailed with the threshold of significance set at  $P < 0.05$ .

Although the patients will be tested at all of the time points. Sample size has been estimated based on Gregersen *et al.*[2] who suggest that 35 patients will be required per group in an unpaired study design to detect a 300kJ difference in overall caloric consumption between two groups with a power of 0.8. We anticipate that single-sitting food intake after upper GI surgery will be approximately 60-80% that of matched controls. Given a control *ad libitum* caloric intake of approximately 600kcal, this would equate to a 120 – 240kcal difference in caloric intake. In addition, differences in preferred food types will be studied.

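### Section 9 plans logistic regression for weight loss without defining a binary outcome, and its univariate screen plus forward stepwise selection overstates the predictors it keeps

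*Combined protocol and SAP*

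**What the plan says.** All the modelling text is in Section 9 (Statistical analysis).

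- Univariate step: factors are related to perioperative and post-surgical weight loss by "Student's *t* test or one-way ANOVA for categorical variables or simple logistic regression for continuous variables".
- Entry rule for the multivariable model: "independent variables which were significant on univariate analysis, including standard demographic, food intake and food preference".
- Multivariable step: a "multiple logistic regression model with a forward stepwise selection procedure to assess their impact on perioperative and post-surgical weight loss".
- Separately, Spearman rank correlation relates intake to perioperative weight loss.
- All tests are two-sided at P<0.05. No multiplicity adjustment, limit on candidates, shrinkage or validation is stated.

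Section 3.2.4 has weight recorded in kilograms and places the measurement at the screening visit. The Section 4 visit lists put it at week -4 ("Anthropometric assessment: Height, weight, BMI and waist circumference"), at week 12 ("Anthropometric Assessment: Height, weight, BMI and waist circumference"), at both week-52 visits and at the final visit. Table 2 does not mark weight at the final visit. No section says which of these weights define either kind of loss, or whether loss is in kilograms, a percentage or BMI units.

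**The concern.** There are two separate problems.

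First, the named model does not fit the outcome. Read literally, someone must choose a cut-off outside the plan, possibly after seeing the data. Categorical and continuous candidates for one model would also be screened on different outcome scales.

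Second, whichever regression is meant, the same patients are used to choose the predictors and to estimate and test them, and only the chosen ones are carried into the final model. A report of predictors of weight loss from this procedure would show effects larger than the truth on average, with P values calculated as if no choice had been made.

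**Working it through.** **1. The text compared.** The plan gives no figure for this analysis to reproduce. Its 35 per group was sized for caloric intake, and is used below only as a plausible number of surgical patients.

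| Use of weight loss in Section 9 | Outcome scale implied |
|---|---|
| t test or ANOVA across categorical factors | continuous |
| Spearman with intake | ranked |
| Simple logistic regression on continuous factors | binary |
| Multiple logistic regression | binary |

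No section supplies the binary definition that the last two rows need. For timing, no study visit is listed between week -4 and week 12, so perioperative loss has no evident pair of weights. Post-surgical loss could refer to week 12, week 52 or the final visit.

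**2. If logistic is meant literally.** Assumptions: n=35, one normally distributed predictor correlated r with weight loss, median split (17 events), likelihood-ratio test, compared with the linear t test on 33 df; 20,000 simulated trials per r.

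| r | Power, logistic | Power, linear |
|---|---|---|
| 0.3 | 30% | 43% |
| 0.4 | 51% | 68% |
| 0.5 | 71% | 89% |

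A median split and an upper-third split reach different conclusions on significance in 21%, 25% and 22% of trials. None of these figures applies if linear regression was intended.

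**3. Why selection inflates.** With n=35 the two-sided 5% critical value is t = 2.035 on 33 df. The smallest sample correlation that passes the screen is t/√(33 + t²) = 2.035/√(33 + 4.14) = 0.334. A predictor with true r=0.3 is therefore kept only in samples that overstate it.

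**4. Size of the inflation.** Assumptions: Y = rX₁ + √(1−r²)e; nine further candidates with no direct effect; common pairwise correlation ρ among the ten; screen at P<0.05, then forward stepwise linear regression with entry P<0.05 and removal P≥0.10. The ratio is the mean slope of X₁ in trials where it is kept, divided by r.

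| r | ρ=0 | ρ=0.5 | ρ=0.7 |
|---|---|---|---|
| 0.3 | 1.47 | 1.55 | 1.56 |
| 0.4 | 1.20 | 1.24 | 1.26 |
| 0.5 | 1.06 | 1.08 | 1.12 |

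A repeat with fresh random numbers agreed within 0.02, with 1.05 as the lowest entry. A logistic version with 10 independent candidates and n=35 points the same way: a true odds ratio of 1.49 per SD is kept in 21% of runs with a median estimate of 2.74, and 2.01 is kept in 47% with a median of 3.06.

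**5. The alternative, on both scales.** Four covariates fixed in advance, linear model, n=35:

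- Over all trials the slope ratio is 0.99 to 1.02 and 95% CI coverage is 94 to 96%.
- Over only those trials where X₁ is significant, the ratio is 1.53/1.85/2.25 at r=0.3 and 1.23/1.44/about 1.7 at r=0.4 (ρ=0/0.5/0.7).
- With no true predictor, at least one P<0.05 occurs in about 15 to 18% of trials (independent-test formula: 1 − 0.95⁴ = 18.5%).
- At r=0.4 the true predictor is significant in 63/45/32% of trials, against 65/50/40% kept by stepwise selection from ten candidates.

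**The case against.** The strongest reply is that logistic is a slip for linear. The t test, ANOVA and Spearman clauses all fit a continuous or ranked outcome. That is plausible, and if so the missing cut-off and all of step 2 fall away. The wording still needs correcting, and the selection problem is unchanged. The missing metric and visit are, on their own, only missing detail.

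A second reply is that the fixed list looks better partly because unlike things are compared: retained-only slopes for stepwise selection, all-trial slopes for the fixed list. This stands. Step 5 shows that significant-only estimates from a fixed list are inflated as much or more. The benefit comes from reporting every estimate and from having fewer candidates.

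Two stronger readings are tempting and should be resisted:

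- A reader might infer that stepwise selection itself creates the high chance of a spurious predictor. With ten independent noise candidates that chance is about 1 − 0.95¹⁰ = 40%, but this is mainly multiplicity. Entering all ten with no selection gives at least one P<0.05 in about 33 to 36% of trials. For correlated candidates (ρ=0.5/0.7) that exceeds the 30/22% under the planned screen.
- A reader might infer that the trial's main conclusions are at risk. Section 2.1 does not support this. The objectives are the effect of surgery on food preference and to "Determine if the changes in food preference following RYGB are mediated through changes in gut peptide following surgery". Weight loss is in neither, and the sample size rests on caloric intake.

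**Conclusion.** The point holds for an ancillary analysis and is worth correcting. The model named in Section 9 does not match any outcome the document defines, and it conflicts with how the same section treats weight loss elsewhere. This rests on the text alone.

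The direction of the selection bias is general and holds for linear and logistic models. Its size rests on assumptions the plan does not supply: 35 patients, 10 candidates, normal variables, one true predictor and the stepwise thresholds. On those assumptions it is about 1.5-fold for a weak predictor and small (1.05 to 1.12) for a strong one. The power loss and cut-off sensitivity are conditional on the literal logistic reading, which is the less likely one.

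**What to change.** In Section 9:

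- Replace both logistic regressions with linear regression of continuous weight loss, using one stated metric at a named visit for all factors.
- State which weights define perioperative loss, or remove the term.
- Drop the univariate screen and forward stepwise selection. Enter in full a short covariate list fixed before analysis.
- Report every estimate with its 95% CI whether or not it is significant, and label the analysis exploratory with no claim of multiplicity control.

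In Section 4, reconcile the final-visit weight between the visit list and Table 2.

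The cost is a few sentences, with no new data or visits. Fewer candidates can be examined. At r=0.4 the chance of identifying a true predictor falls by 2, 5 and 8 percentage points (65−63, 50−45, 40−32) as candidate correlation rises through 0, 0.5 and 0.7.

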### ***2.2 Design***

The Study will be conducted in two parts. The first phase of the study is an observational component where participants who are due to undergo RYGB surgery in addition to a matched control group will have their food preference assessed using a standardised macronutrient self selection paradigm (MSSP). This process will be undertaken 1 months pre and 3, 12 and 24 months post surgical intervention (See figure 1). The control group will be studied at matched time points. This will allow determination of the primary outcome, whether RYGB surgery alters food preference. Phase two of the trial will focus on understanding potential mechanisms responsible for altered food preference. It will take the form of a randomised control study whereby subjects following RYGB and controls will be

invited to repeat the MSSP after randomly receiving octreotide or saline placebo in a blinded crossover fashion. This assessment will take place one year following surgery.

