### **3.5 Buffet Meal**

The study will take place at the Clinical Research Centre at St Vincents University Hospital. The study methodology will follow the paradigm for food preference assessment developed and validated by Geiselman *et al* [1].

Subjects will be provided with a Food preference questionnaire prior to the study visit. This will ask patients to hedonically/by preference rate each of approximately 90 common foodstuffs of known macronutrient composition on a 9-point Likert scale with the following anchors: 1 = dislike extremely; 5 = neutral; 9 = like extremely. This assessment will be completed by subjects prior to their screening visit, the data sheet will be collected and evaluated by the research investigator. This food preference questionnaire will categorise the 90 food stuffs into each of the 6 cells highlighted in the table below and in no particular order.

Responses from the questionnaire will be used to select appropriate foodstuffs for use in an 18 item buffet spread, for each given subject, from the stock list of 90 items. The 18 items selected for the buffet spread will comprise high fat and low fat options combined with varying carbohydrate and protein content, as depicted in **Table 1**. We will endeavour to provide each subject with foods to which he/she had an intermediate hedonic response (5 – 7). High fat foods given to an individual subject will be paired with a low fat variation of the same food; eg high and low fat meat options, high and low fat cheese options. Stock list foods are all items which are commercially available and require minimal or no preparation (for example slicing fruit, bread or cheese). All food items will be stored and used according to manufacturer’s instructions.

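### Section 9 tests every comparison at an unadjusted P < 0.05 and names no primary preference variable or visit, so the error rate for the primary claim is not held at 5%.

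*Combined protocol and SAP*

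**What the plan says.** Section 2.1 lists two primary objectives. The first is "Determine the effect of Roux-en-Y gastric bypass (RYGB) surgery on food preference using a standardised Buffet meal", and the second is "Determine if the changes in food preference following RYGB are mediated through changes in gut peptide following surgery". Section 2.2 ties the primary outcome to the first of these: "This will allow determination of the primary outcome, whether RYGB surgery alters food preference". It sets the assessments as follows: "This process will be undertaken 1 months pre and 3, 12 and 24 months post surgical intervention".

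Section 3.5 sorts the foods into six classes: "This food preference questionnaire will categorise the 90 food stuffs into each of the 6 cells highlighted in the table below". Table 1 crosses two fat levels with three carbohydrate/protein types.

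Section 9 plans the group comparison in general terms: "Differences in continuous variables between surgical and control groups will be calculated using the Student's" t test or the Mann-Whitney U test. It mentions caloric intake and macronutrient intake, and adds that preferred food types will be examined. It then closes with "All statistical analyses will be two-tailed with the threshold of significance set at" P < 0.05. It does not count or rank the tests, and it does not say which variable or visit decides the primary outcome. The sample size of 35 per group refers only to total energy intake.

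**The concern.** A 5% threshold gives a 5% false-positive rate for a claim only when one test decides that claim. Here the primary outcome is a concept. It can be examined at 3, 12 and 24 months, on fat, carbohydrate and protein intake or on up to six food classes. Nothing in the plan says which of these results would establish that RYGB alters food preference, or how a mixed pattern would be read. If one favourable comparison among many can carry the conclusion, the error rate for the primary claim exceeds 5% by an amount that depends on choices the plan leaves open. Those choices could be made after the data are seen. A reader of the eventual report could not tell whether a significant result was the planned test or one of many.

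**Working it through.** **The plan's own figure.** The plan gives 35 per group, a 300 kJ difference and power 0.8, but no SD, so the figure cannot be reproduced independently. Solving backwards at two-sided 0.05:

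- Normal approximation: SD = 300 / [(1.960 + 0.842) × √(2/35)] = 300 / 0.670 ≈ 448 kJ.
- Noncentral t: the detectable difference at 35 per group is 0.679 SD, so SD = 300 / 0.679 ≈ 442 kJ.

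The calculation allows for one test of one variable, total energy intake. It includes nothing for multiple preference tests.

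**Inputs for the error rate.**
- Per-test level 0.05, two-sided (Section 9).
- Three post-surgery visits in the same people (Section 2.2).
- Number of preference variables: not stated. I take 1, 3 (three macronutrients) and 6 (all cells of Table 1) as scenarios.
- Between-visit correlation: not stated. I assume 0.5 to 0.9, with independence as the upper case.

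**Independent tests.** The chance of at least one false positive among k true nulls is 1 − 0.95^k.
- k = 3 (1 variable × 3 visits): 1 − 0.95³ = 14.3%
- k = 9 (3 × 3): 1 − 0.95⁹ = 37.0%
- k = 18 (6 × 3): 1 − 0.95¹⁸ = 60.3%

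**Correlated tests.** Independence is not realistic: the same people return at each visit and, if intake is expressed as shares, the shares must sum to a constant. I simulated 100,000 sets of normal test statistics under no effect. The variables were either independent of one another or shares with pairwise correlation −1/(m − 1) for m classes.

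| Family | Independent | Visit correlation 0.5 | Visit correlation 0.9 |
|---|---|---|---|
| 1 variable × 3 visits | 14.3% | 12.5% | 8.3% |
| 3 macronutrients × 3 visits | 37.0% | 33% (shares 29%) | 23% (shares 19.5%) |
| 6 cells × 3 visits | 60.3% | 55% (shares 53%) | 41% (shares 38%) |

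Every scenario is above 5%, including the mildest.

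**How many tests make a false claim an even chance?** log(0.5) / log(0.95) = 13.5, so about 14 independent tests. Among these scenarios, only six cells at three visits comes near it.

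**Power cost of adjustment.** At 35 per group and power 0.8 (noncentral t), the detectable difference is:
- 0.68 SD at 0.05
- 0.79 SD at 0.05/3 = 0.0167
- 0.95 SD at 0.05/18 = 0.0028

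**The case against.** The strongest reply is that the plan neither promises familywise control nor states that one significant cell at one visit would settle the question. Phase one is observational, and strict adjustment over everything measured is only one convention. The six cells are described as a way of choosing buffet foods, not as six endpoints. All of this is fair. It means the plan has a gap, not a stated any-one-result rule, and the 18-test figure is a scenario, not a description of what will be done.

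A reader might infer that a false claim is about as likely as not. The documents do not support that. It needs roughly 14 independent tests, or all six cells tested at all three visits, together with a rule that any one result suffices.

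A reader might also count the second primary objective as another route to the same false claim and cite 1 − 0.95² = 9.75%. That figure covers the two primary hypotheses taken together. A false positive on gut-peptide mediation cannot produce a false claim that RYGB alters preference.

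The no-effect assumption also has a limit. Section 9 expects single-sitting intake after surgery to be 60-80% of that of controls. If absolute macronutrient intakes are tested, many would differ simply because total intake falls. The null scenario suits measures of composition, such as percentage of energy, better than absolute amounts.

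What remains is that nothing in the plan limits the tests behind the primary claim, and the mildest scenario still exceeds 5%.

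**Conclusion.** The concern holds in a limited form: multiplicity within the first primary objective is uncontrolled. The false-claim rate is about 8-14% for one variable at three visits, 19-37% for three macronutrients and 38-60% for all six cells. These ranges rest on three assumptions: no true effect on any tested variable, any single significant result being reported as the claim, and between-visit correlation running from 0 (high end) to 0.9 (low end, with shares summing to a constant for the three- and six-variable families). The documents fix neither the number of tests nor the claim rule, so the defect is certain and its size is not. It should be corrected because the remedy is mainly a matter of specification.

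**What to change.** Revise Section 9 as follows.

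1. Name one primary preference variable (for example, percentage of energy from fat) and one primary post-surgery visit. Test the surgical-control difference there at two-sided 0.05, and let the primary claim rest on that test. If 12 months is chosen, state which of the two buffet visits at that time point supplies the data.
2. Report Holm-adjusted P values for that variable at the other visits and for a short, named list of other preference variables. Holm is valid under any correlation among the tests. An unnamed list would leave the family as open as it is now.
3. Keep total energy intake, the only variable the sample size addresses, as a separate named endpoint with its own stated place in the testing order. If it follows the primary test in sequence, its claim depends on that test. If it stands beside it as a second primary claim, the 5% must be shared.
4. Report the correlations and weight-loss models as exploratory, with 95% confidence intervals.
5. Treat objective 2 as a separate mechanistic question. It should not count as evidence that RYGB alters preference. Nor should a non-significant result on objective 1 be read as proof that there is no change to explain.

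No visits or data are added. The cost is power for the non-primary tests: at 35 per group the difference detectable with 80% power rises from 0.68 SD to 0.79 SD at the first Holm step over three tests. It would reach 0.95 SD over 18, which is the reason to keep the list short. The primary test keeps its full 0.05.

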## ***10 Duration of Project***

The estimated duration of the study will be 36 months. Screening and recruitment will begin in February 2016. Completion of the study is planned for February 2019.

## ***11 Administrative considerations***

### ***11.1 Changes to the conduct of the study/Amendments to study protocol***

Any and all amendments to the protocol must be agreed upon by the named investigators of the study. All protocol amendments must be submitted to the institutional ethics committee for approval. Informed consent documents must be updated with amendments appropriately and submitted with application for protocol revision. Changes to the protocol may not be implemented prior to ethical approval unless it is intended to eliminate an immediate hazard to the study subject. In this case study sponsor and ethics committee must be informed as soon as possible of the deviation.

### ***11.2 Premature termination of the study***

The principal investigator reserves the right to terminate the study at any time. Adequate consideration must be given to the protection of all study volunteers on termination of the investigation. Subjects will be informed in writing immediately and appropriate follow-up is assured.

